4.4.2 Subgroup Analyses

Comparative subgroup analyses describing the bleed rate (treated and all) will be conducted. In addition, estimated ABR including 95% confidence interval will be calculated in each subgroup. Note that due to the small sample size, all subgroup analyses will be highly sensitive to variability caused by individual patients and need to be interpreted with caution.

The pre-specified subgroups are:

- Age: 0 to <2, 2 to <6, 6 to <12, \geq 12 years
- Race: Asian, Black or African American, White, Other
- Pre-study hemophilia treatment type: Episodic versus Prophylactic
- Number of target joints at baseline: no target joint, any target joint

In addition, region- and/or country-specific analyses will be performed to support regulatory submissions as needed.

These subgroup analyses will not be performed at the time of the interim analyses. For the Primary CSR, these analyses will be performed for the all patients population regardless of the dosing regimen as sample size will be too small per regimen.

4.5 PHARMACOKINETIC ANALYSES

For all patients, pre-dose (trough) plasma concentrations of emicizumab will be presented descriptively at each timepoint by dose group, including arithmetic and geometric means, median, range, standard deviations, and coefficients of variation.

Nonlinear mixed effects modeling will be used to analyze the dose-concentration-time data of emicizumab following SC administration. Population PK parameters, such as clearance and volume of distribution, will be estimated, and the influence of various covariates, such as age and body weight, on these parameters will be investigated graphically. Secondary PK parameters, such as area under the curve, will be derived from individual post-hoc predictions. Data may be pooled with data from previous Phase I/II studies and Study BH29884. These analyses will be reported in a dedicated report.

In addition, region- and/or country-specific analyses will be performed to support regulatory submissions as needed (e.g., PK analysis in Japanese vs. non-Japanese patients or analyses based on ethnicity).

The PK will be analyzed separately for the three cohorts: Cohort A (1.5 mg/kg/QW), Cohort B (3 mg/kg/ Q2W), and Cohort C (6 mg/kg Q4W).

4.6 SAFETY ANALYSES

Safety will be assessed through descriptive summaries of adverse events, laboratory test results (including serum chemistry, hematology, coagulation, and antibodies to emicizumab), ECGs, and vital signs.

4.6.1 Exposure to Study Medication

Information on study drug administration will be summarized by duration and cumulative dose. In addition, treatment exposure will be summarized including delays and interruptions. The number of patients whose dose was up-titrated will be summarized.

Patient withdrawals from study treatment will be reported in listings and summary tables.

4.6.2 Adverse Events

To evaluate the overall safety of prophylactic emicizumab, adverse events will be summarized and presented by System Organ Class mapped term, appropriate thesaurus level, and toxicity grade (WHO Criteria). All AEs will be coded using the current version of MedDRA at the time of each database closure (interim and primary analysis). For the purpose of summarization, a patient is counted once in a system organ class or preferred term if the patient reported one or more events in that system organ class or preferred term. Percentages will be based on the number of patients overall.

The total number and percentage of patients with at least one AE and total number of AEs will be summarized. Separate AE summaries for SAEs, AESIs, severity, relatedness, and discontinuation/modification will be provided.

An overall summary of adverse events (including SAEs, AESIs, AEs leading to drug discontinuation, and deaths), which tabulates the number and percentage of patients who experienced any or serious adverse events and the number and percentage of patients who died, will be provided.

For adverse events with a missing intensity, seriousness, or relationship, the worst case will be assumed and the adverse events will be considered life-threatening (Grade 4) or serious.

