2.2 SAFETY OBJECTIVE

The endpoints will be analyzed separately for the three cohorts: Cohort A (1.5 mg/kg QW), Cohort B (3 mg/kg Q2W), and Cohort C (6 mg/kg Q4W), and overall as appropriate.

The safety objective for this study is to evaluate the overall safety of emicizumab in pediatric patients with hemophilia A and inhibitors on the basis of the following endpoints:

- Incidence and severity of adverse events
- Incidence and severity of thromboembolic events
- Changes in physical examination findings and vital signs
- Incidence of laboratory abnormalities
- Incidence and severity of injection-site reactions
- Incidence of adverse events leading to drug discontinuation
- Incidence of severe hypersensitivity, anaphylaxis, and anaphylactoid events
- Incidence and severity of TMA
- Incidence and clinical significance of anti-emicizumab antibodies

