3.2 END OF STUDY AND LENGTH OF STUDY

LENGTH OF STUDY

The length of the entire study from screening of the first patient to the last patient completing 52 weeks in the study and/or the end of study follow-up visit (24 weeks after discontinuing emicizumab) will be approximately 152 weeks.

END OF STUDY

The primary analysis will take place at the same time for Cohorts A, B, and C. It will occur after all patients in the primary population of Cohort A have completed 52 weeks of treatment, or have withdrawn prematurely, whichever occurs first. All data from patients enrolled in Cohorts B and C will be included regardless of follow-up time.

After 52 weeks of treatment, an individual patient who continues to derive clinical benefit may continue receiving prophylactic emicizumab as part of this study or a future

separate emicizumab extension study. Patients who discontinue emicizumab will have a safety follow-up visit at 24 weeks after the last emicizumab dose.

The end of this study is defined as the date when the last remaining patient has completed the last visit (i.e., LPLV), as defined below:

- Completed 52 weeks of emicizumab and either transferred to a separate extension study to receive further emicizumab as per Roche Global Policy on Continued Access to Investigational Medicinal Products or to commercial product

OR

- Completed the end of study safety follow-up visit 24 weeks after discontinuing emicizumab

OR

- Consent has been withdrawn

OR

- Lost to follow-up

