4.5.2 Dosage, Administration, and Compliance

Emicizumab treatment will begin with a loading dose of 3 mg/kg QW for the first 4 weeks (Day 1 of each week) followed on Week 5 by a maintenance dose of either 1.5 mg/kg QW (Cohort A), 3 mg/kg Q2W (Cohort B), or 6 mg/kg Q4W (Cohort C). Note that the cumulative dose studied in all three cohorts is identical, but the dose administration schedule differs between cohorts. Patients will receive prophylactic emicizumab for a minimum of 52 weeks, or until unacceptable toxicity or discontinuation from the study due to any cause.

On 7 December 2016, the JMC recommended continued enrollment to Cohort A at the original starting maintenance dose of 1.5 mg/kg QW, and to open enrollment to patients < 2 years of age at that same maintenance dose. Moreover, review of data in adults and adolescents from two ongoing Phase III studies evaluating emicizumab at 3 mg/kg Q2W (BH30071) and 6 mg/kg Q4W (BO39182) has identified no safety concerns to date. See Section 3.3.1.1 for details.

During the 52-week treatment period, individual patients may have their dose up-titrated if they experience suboptimal bleeding control on emicizumab. *Patients in Cohorts A, B, or C with ≥ 2 qualifying bleeds within a 12-week interval may have the opportunity to have their maintenance emicizumab dose increased to 3 mg/kg QW starting on Week 17, if they receive approval from the Medical Monitor. Of note, for patients from Cohorts B or C who have a dose up-titration, their dosing regimen will change from Q2W or Q4W to QW. Qualifying bleeds are defined as spontaneous and clinically significant, physician verified (e.g., with diagnostic imaging, clinical examination, photograph), and occurring while on prophylactic emicizumab at steady-state on the maintenance dose (after Week 5). Should patients meet protocol-defined criteria for up-titration, the investigator will contact the Medical Monitor to initiate a discussion about possible up-titration. Upon up-titration to the new maintenance dose of 3 mg/kg QW, the patient's schedule of assessments will reset to Week 1, and the next five visits must take place at the site.*

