5.3.5.1 Injection-Site Reactions

Local adverse events that occur within 24 hours after study drug administration and are judged to be related to study drug injection should be captured as an "injection-site reaction" on the Adverse Event eCRF. Associated signs and symptoms (e.g., injection-site erythema or injection-site rash) should be recorded on the dedicated Injection-Site Reaction eCRF. If a patient experiences both a local and systemic reaction to the same administration of study drug, each reaction should be recorded separately on the Adverse Event eCRF. Only for local injection-site reactions should the dedicated Injection-Site Reaction eCRF be used to capture the individual signs/symptoms.

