4.1 OUTPUT LAYOUTS

The key output layout is designed to address the study objectives in a flexible manner and provide an overall view of the efficacy and safety of emicizumab for all dosing regimens. The key output layout is as follows:

All patients: these outputs will provide an overall view of all the data collected under emicizumab prophylaxis. Patients will be grouped according to their original maintenance regimen at study entry (QW, Q2W and Q4W) with a total column provided as well.

Listings will include all the data for all the patients with a flag indicating the dose related to each event and the dosing regimen of the patients. As appropriate, outputs will be produced for each dosing regimen separately.

Patients may be allowed to up-titrate their emicizumab dose if they meet the pre-specified criteria as described in the protocol. Patients will be grouped according to their original maintenance dose at study entry.

The data under the new, higher dose will be analysed and reported separately. Additional summaries will be produced for key safety and exposure on all data (i.e., data before and after up-titration).

For Cohort A, the primary set of outputs will include patients from 0 to < 12 years of age. Three additional limited sets of outputs will be produced: one for patients \geq 12 years of age, one for the combined sets (0 to < 12 years of age and \geq 12 years of age) and one for patients \leq 2 years old at time of enrolment.

For Cohorts B and C, only one set of outputs will be produced for each cohort and will include all the patients enrolled in these cohorts.

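### Injection-site reactions have no per-administration measure, so the regimen columns will partly reflect how many doses each schedule gives (52, 28 and 16 for QW, Q2W and Q4W over an equal 52 weeks)

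*SAP*

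**What the plan says.** Protocol 2.2 lists "Incidence and severity of injection-site reactions" among the safety endpoints, to be analysed separately for the three cohorts and overall as appropriate. Protocol 5.3.5.1 restricts what is recorded as an ISR: "Local adverse events that occur within 24 hours after study drug administration and are judged to be related to study drug injection".

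SAP 4.6.2 sets the counting rule for adverse events: "a patient is counted once in a system organ class or preferred term if the patient reported one or more events". Percentages use the number of patients as denominator. The total number of events is also tabulated, without a dose denominator. SAP 4.1 places the regimens side by side: "Patients will be grouped according to their original maintenance regimen at study entry (QW, Q2W and Q4W"), with a total column.

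SAP 4.6.1 summarises exposure by duration and cumulative dose, with delays and interruptions. It does not list the number of administrations. Protocol 4.5.2 says of the three regimens: "Note that the cumulative dose studied in all three cohorts is identical". The SAP contains no analysis specific to ISRs and none per administration.

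**The concern.** A child can have a recorded ISR only in the day after a dose. Two regimens with the same risk per dose but different numbers of doses will therefore give different percentages of children with at least one ISR. The three regimens differ in exactly this respect, and the planned exposure summary does not show it, because cumulative dose is the same in every column by design.

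Cohorts B and C were added so that a preferred schedule could be chosen, and each of their maintenance doses is two or four times the QW dose. Whether the larger dose is tolerated as well locally, administration for administration, is a natural question for readers of these tables. The patient percentage does not address it. Equal tolerability per administration would tend to appear as an advantage for Q2W and Q4W, and a real increase per administration on Q4W could be hidden behind its smaller number of doses.

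**Working it through.** **Inputs.** Protocol 4.5.2: four weekly loading doses of 3 mg/kg in all cohorts, then from Week 5 maintenance of 1.5 mg/kg every week, 3 mg/kg every 2 weeks or 6 mg/kg every 4 weeks. Protocol 3.2: the primary analysis comes "after all patients in the primary population of Cohort A have completed 52 weeks of treatment" or have withdrawn. Protocol 3.1: Cohorts B and C then have an efficacy period of about 6 months, taken here as 26 weeks. Planned sizes are about 60 / 10 / 10. No document gives an ISR risk per dose. Protocol 1.2 reports 7 of 18 Phase I/II patients (38.9%) with an ISR, which is a patient-level figure. The risks used below, 0.5% to 2% per administration, are assumptions.

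**The plan's own figure.** Cumulative dose over 52 weeks is 4 × 3 = 12 mg/kg of loading plus maintenance:
- A: 12 + 48 × 1.5 = 84 mg/kg
- B: 12 + 24 × 3 = 84 mg/kg
- C: 12 + 12 × 6 = 84 mg/kg

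The statement that cumulative dose is identical is reproduced. It also shows that cumulative dose cannot reveal the difference in number of doses.

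**Administrations** = 4 + maintenance doses from Week 5.
- By Week 52: 4 + 48 = 52, 4 + 24 = 28, 4 + 12 = 16. QW to Q4W ratio: 52/16 = 3.25.
- By Week 26: 26, 15, 10. Ratio: 26/10 = 2.6.
- At the primary analysis (A at 52 weeks, B and C at 26): 52, 15, 10. Ratio: 52/10 = 5.2. This combines schedule with unequal follow-up.

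**Expected percentage with at least one ISR at equal risk p per administration.** With independence this is 1 − (1 − p)^n. With within-child correlation ρ (beta-binomial) it is 1 − B(a, b + n)/B(a, b), where a = p(1 − ρ)/ρ and b = (1 − p)(1 − ρ)/ρ.

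| Assumed p, ρ | Equal 52 weeks, QW / Q2W / Q4W | Primary analysis, QW / Q2W / Q4W |
|---|---|---|
| 0.5%, 0 | 22.9 / 13.1 / 7.7% | 22.9 / 7.2 / 4.9% |
| 1%, 0 | 40.7 / 24.5 / 14.9% | 40.7 / 14.0 / 9.6% |
| 2%, 0 | 65.0 / 43.2 / 27.6% | 65.0 / 26.1 / 18.3% |
| 1%, 0.2 | 10.5 / 8.4 / 6.6% | 10.5 / 6.4 / 5.3% |
| 2%, 0.2 | 19.9 / 16.2 / 12.9% | 19.9 / 12.5 / 10.3% |

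If reactions arose only during the four loading doses, every cohort would have the same expectation (1 − 0.98^4 = 7.8% at 2%) and there would be no gap.

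**Chance that the observed QW percentage exceeds the Q4W percentage** (60 and 10 patients, equal risk of 1%, primary analysis): 0.99 with independence, 0.73 with ρ = 0.2.

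**Masking.** With a QW risk of 2% and independence, the Q4W risk giving the same patient percentage is 1 − 0.98^(52/16) = 6.4% at equal 52 weeks, and 1 − 0.98^(52/10) = 10.0% at the primary analysis.

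**Rates per patient-year do not repair this.** At 2% they are 52 × 0.02 = 1.04, 28 × 0.02 = 0.56 and 16 × 0.02 = 0.32. ISRs per 100 administrations would be 2.0 in all three cohorts.

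**Precision of the remedy.** By Week 26 Cohort C has 6 × 10 = 60 maintenance doses. At 2% that is 1.2 expected reactions, with a 0.98^60 = 30% chance of none. One reaction would give a Poisson 95% interval of about 0.04 to 9.3 per 100 administrations, before any allowance for clustering.

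**The case against.** The endpoint is incidence, and a patient-level percentage is a direct answer to it. At equal follow-up, fewer reactions because of fewer doses is a real property of a regimen, and it matters to a family choosing a schedule. That stands: the percentage is a valid burden measure. What it does not measure is tolerability per administration.

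Other planned output helps. SAP 4.6.2 gives total event counts, SAP 4.6.1 gives duration, and SAP 4.1 plans listings that flag the dose related to each event. With a fixed schedule, a careful reader could assemble a rough rate. That also stands, but the plan leaves the calculation to the reader and does not tabulate the denominator.

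The study is descriptive and non-randomised, and the Phase I/II ISRs were all mild. This is a matter of presentation, not a testing error.

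A reader might go further in three ways that the documents do not support:
- **That dosing frequency alone creates a five-fold difference.** The 5.2 ratio includes the shorter follow-up of Cohorts B and C at the primary analysis. The schedule alone gives 3.25 over 52 weeks and cannot exceed 4. SAP 2.5 also plans a final analysis at study end.
- **That Q2W and Q4W will look better tolerated.** This depends on an assumed constant risk and limited clustering, with about 10 children in each of those cohorts.
- **That the comparison can be made per injection.** Protocol 4.5.2 implies that heavier children may need more than one injection per dose, and Protocol 3.1 describes the device as recording total volume and date/time. At 150 mg/mL a child of 39.9 kg needs 0.4 mL for a QW dose and 1.6 mL for a Q4W dose. The supportable unit is the administration.

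**Conclusion.** The concern holds as a presentation gap in a named safety endpoint. The regimen columns will compare percentages resting on 52 / 28 / 16 administrations at an equal 52 weeks, and on 52 / 15 / 10 at the primary analysis, with no measure per administration beside them. Cohort A children followed beyond 52 weeks would widen the latter contrast.

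With equal and independent risk of 0.5% to 2% per administration, the expected QW to Q4W contrast is 23% to 8% up to 65% to 28% at equal follow-up, and 23% to 5% up to 65% to 18% at the primary analysis. The direction survives strong clustering, but the size does not: at 2% and ρ = 0.2 the equal-follow-up contrast is 20% to 13%. Lower percentages for Q2W and Q4W are an expectation, not a certainty, and a higher risk per administration on Q4W could go unseen.

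A reader might infer that a rate per administration would settle whether the larger doses are tolerated as well. It would not: about 60 Cohort C maintenance doses by Week 26 are too few. It would remove a predictable distortion and show the uncertainty openly.

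**What to change.** In SAP 4.6.1, add the number of emicizumab administrations per patient, summarised by regimen.

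In SAP 4.6.2, add that ISRs will also be presented by regimen as the number of reactions per 100 emicizumab administrations, with a 95% confidence interval allowing for repeated events within patient, for all doses and for maintenance doses only. The maintenance-only rate separates the regimens from the loading phase they share. Name the interval method and a fallback for cohorts with no or very few events. Count reactions and administrations over the same period; SAP 4.1 already reports data after up-titration separately.

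Keep the patient percentage, with a footnote that it depends on the number of administrations and on follow-up. State that the Cohort B and C estimates are descriptive and imprecise, and use the term per administration throughout.

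The cost is a few lines of SAP text, one exposure row and one table. No new data are needed: dosing is entered on the handheld device (Protocol 4.5.2), and reactions are on the Adverse Event and Injection-Site Reaction eCRFs (Protocol 5.3.5.1). The only drawback is wide intervals in Cohorts B and C.

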4.6.3 Laboratory Data

For clinical laboratory data, which were collected from local laboratories, summary statistics in SI units will be presented. Laboratory data not collected in SI units will be converted to SI units as applicable. In addition, shift tables describing changes from baseline will be presented using the WHO toxicity grading scale.

Data on the impact of immunogenicity (anti-emicizumab antibodies) on safety, efficacy, and/or clinical pharmacology and pharmacokinetics will be summarized using standard language/terminology ([Shankar et al. 2014](#)).

4.6.4 Vital Signs

Vital signs will be summarized using mean change from baseline tables over time. Measurements consist of heart and respiratory rate, temperature, and systolic and diastolic blood pressure.

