4.7.4 Vital Signs

Vital signs will include measurement of pulse and respiratory rate, temperature (oral, rectal, axillary, or tympanic), systolic and diastolic blood pressure using age-adapted measurements, height/length and weight and should be recorded before study drug administration. Frequency of vital sign assessments should follow the schedule of assessments (see [Appendix 1](#)) but may also be taken any time as unscheduled assessments as judged by the investigator.

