Appendix 6 **Clinical Criteria for Diagnosing Anaphylaxis**

These criteria are taken from a summary report from the second symposium on the definition and management of anaphylaxis, conducted by the National Institute of Allergy and Infectious Disease/Food Allergy and Anaphylaxis Network.¹ Anaphylaxis is highly likely when any one of the following three criteria is fulfilled:

1. Acute onset of an illness (minutes to several hours) with involvement of the skin, mucosal tissue, or both (e.g., generalized hives, pruritus or flushing, swollen lips, tongue/uvula)

AND AT LEAST ONE OF THE FOLLOWING:

- Respiratory compromise (e.g., dyspnea, wheeze-bronchospasm, stridor, reduced peak expiratory flow, hypoxemia)
 - Reduced blood pressure or associated symptoms of end-organ dysfunction (e.g., hypotonia, syncope, incontinence)
2. Two or more of the following that occur rapidly after exposure to a likely allergen for that patient (minutes to several hours):
 - Involvement of the skin-mucosal tissue (e.g., generalized hives, itch-flush, swollen lips-tongue-uvula)
 - Respiratory compromise (e.g., dyspnea, wheeze-bronchospasm, stridor, reduced peak expiratory flow, hypoxemia)
 - Reduced blood pressure or associated symptoms (e.g., hypotonia, syncope, incontinence)
 - Persistent gastrointestinal symptoms (e.g., crampy abdominal pain, vomiting)
 3. Reduced blood pressure after exposure to known allergen for that patient (minutes to several hours):
 - Infants and children: low systolic blood pressure (age specific) or greater than 30% decrease in systolic blood pressure²
 - Adults: systolic blood pressure of less than 90 mmHg or greater than 30% decrease from that person's baseline

¹ Sampson HA, Muñoz-Furlong A, Campbell RL, et al. Second symposium on the definition and management of anaphylaxis: summary report—second National Institute of Allergy and Infectious Disease/Food Allergy and Anaphylaxis Network symposium. *J Allergy Clin Immunol* 2006;117:391–7.

² Low systolic blood pressure for children is defined as less than 70 mmHg from 1 month to 1 year, less than (70 mmHg + [2 x age]) from 1 to 10 years, and less than 90 mmHg from 11 to 17 years.

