- ^d A complete physical examination will be performed at screening and targeted physical examination will be performed at subsequent visits. Targeted physical examination of joints (for bleeds, evidence of arthropathy) and skin (for bruises, hematomas, and injection-site reactions), in addition to other organ systems as clinically indicated and/or report of new or worsening adverse event.
- ^e Body temperature (oral, rectal, axillary, or tympanic), blood pressure, pulse rate, respiratory rate, height/length, and weight to be entered into eCRF. If Screening and Week 1 occur on the same date, the vital signs should be measured only once. If Screening and Week 1 occur on different dates, vital signs should be repeated for both assessments.
- ^f Concomitant medications (e.g., extra pain medication with bleed) will be asked about at each clinic visit and documented in the eCRF, excluding treatments for bleeds (i.e., bypassing agents and other medications to treat bleeds), which will be collected on the bleed/medication questionnaire. Hemostatic medications to treat or prevent bleeds in the 4 weeks prior to starting emicizumab will be collected on eCRF.
- ^g If screening ECG abnormal, repeat at Week 1 (or Week 2 if Screening and Week 1 occur on the same date). ECGs will also be performed 4 weeks after starting emicizumab or after each dose up-titration, as well as at study completion/early termination.
- ^h In case of up-titration, additional assessments including PK, PD biomarkers, anti-emicizumab antibodies, safety laboratory samples, and ECG will be required, with the schedule of assessments resetting back to Week 1, including an ECG.

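### SAP 4.6.4 leaves out height/length and weight, which the protocol counts as vital signs, and plans no count of children with values abnormal for their age

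*SAP*

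**What the plan says.** Protocol 2.2 lists among the safety endpoints "Changes in physical examination findings and vital signs". Protocol 4.7.4 defines the term. It opens with "Vital signs will include measurement of pulse and respiratory rate, temperature (oral, rectal, axillary, or tympanic), systolic and diastolic blood pressure using age-adapted" measurements, and the same sentence goes on to "height/length and weight and should be recorded before study drug administration". The schedule of assessments marks vital signs at screening and at every on-treatment visit to Week 49, then every 12 weeks from Week 57. The footnote to that row, reproduced in SAP Appendix 2, repeats the definition: "blood pressure, pulse rate, respiratory rate, height/length, and weight to be entered into eCRF".

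SAP 4.6.4 has two sentences. The method: "Vital signs will be summarized using mean change from baseline tables over time". The content: "Measurements consist of heart and respiratory rate, temperature, and systolic and diastolic blood pressure".

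**The concern.** The second sentence of SAP 4.6.4 reads as a complete list, and it is shorter than the list in the protocol and in the SAP's own appendix. A programmer who follows it will produce no summary of height/length or weight after baseline, so the protocol's endpoint is only partly delivered. The trial enrols children from birth and treats them for at least 52 weeks.

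The method is also thin for this age range. The primary outputs for Cohort A combine ages 0 to under 12 years (SAP 4.1). A raw mean change mixes ordinary maturation with any effect of treatment, and it cannot say how many children had a value abnormal for their age. Laboratory data get shift tables by toxicity grade (SAP 4.6.3); vital signs get no comparable table.

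**Working it through.** The plan gives no figure on this point, so there is none to reproduce. The check compares the texts and adds two short illustrations.

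**1. The two lists**

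| Measurement | Protocol 4.7.4 | SAP 4.6.4 |
|---|---|---|
| Pulse / heart rate | yes | yes |
| Respiratory rate | yes | yes |
| Temperature | yes | yes |
| Systolic pressure | yes | yes |
| Diastolic pressure | yes | yes |
| Height/length | yes | no |
| Weight | yes | no |

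Seven measurements are defined and five are summarised: 7 - 5 = 2 omitted.

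**2. Is the gap filled elsewhere?** Weight is a baseline characteristic in Protocol 6.3, a trigger for recalculating dose volume in Protocol 4.5.2, and a covariate examined graphically in the PK model (Protocol 6.6, SAP 4.5). None of these summarises weight over time. Height/length is not analysed anywhere.

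**3. How far one child moves a mean.** Shift = individual change / n. The individual change is an assumption (20 to 40 mmHg; the documents give none). The group sizes are the planned ones in SAP 2.4.

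- About 60 patients (Cohort A): 20/60 = 0.33 to 40/60 = 0.67 mmHg.
- About 10 patients (Cohort B or C): 20/10 = 2 to 40/10 = 4 mmHg.

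A single marked change would not be noticed in the Cohort A mean. It could show in the mean of a 10-patient cohort.

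**4. Why a raw value needs the child's age beside it.** Protocol Appendix 6 is the only place with age-specific pressure limits: "Low systolic blood pressure for children is defined as less than 70 mmHg from 1 month to 1 year", then 70 + 2 x age from 1 to 10 years, then 90 mmHg from 11 to 17 years.

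- Age 2: 70 + 2 x 2 = 74 mmHg.
- Age 6: 70 + 2 x 6 = 82 mmHg.
- Age 10: 70 + 2 x 10 = 90 mmHg.

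The limit spans 90 - 74 = 16 mmHg between ages 2 and 10, and 90 - 70 = 20 mmHg from infancy to 17 years. By this rule, 80 mmHg is low at age 6 and not low at age 2. An unstandardised table or range cannot tell those two children apart.

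**The case against.** The strongest reply is that the plan already keeps individual values in view:

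- SAP 4 promises medians, ranges and standard deviations for continuous variables.
- SAP 4.1 promises patient-level listings of all data.
- Protocol 5.3.5.6 requires an abnormal vital sign to be reported as an adverse event when it has symptoms, changes treatment, prompts an intervention or is judged clinically significant.
- SAP 4.6.2 tabulates those events by WHO grade, and the WHO scale in Protocol Appendix 5 has rows for hypertension, hypotension and fever.

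This stands. A reader might infer from SAP 4.6.4 that one child's abnormal value disappears into the average; the documents do not support that. What these routes do not give is a systematic count by age. A range or listing shows the raw value and leaves the age comparison to the reader, and adverse event reporting depends on consequences or on the investigator's judgement. None of them yields a summary of height or weight over time.

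A reader might also infer that a growth endpoint has been dropped. No objective in Protocol Section 2 mentions growth. What is incomplete is the summary of vital signs as the protocol defines them, and standardised growth scores go somewhat beyond restoring it.

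Nor should the Appendix 6 limits be read as evidence of drift in the mean-change table. Change from baseline removes differences in level between children. The 2 mmHg per year is the slope of a diagnostic cutoff, is not shown to be the yearly rise in average pressure, and is flat at 90 mmHg from age 11. The limits are given for diagnosing anaphylaxis, whereas scheduled vital signs are taken before dosing.

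Finally, follow-up at the primary analysis will be short for some children. Protocol 3.1 includes late-enrolled children under 2 years whatever their follow-up and expects about 6 months of efficacy data in Cohorts B and C. That limits what the added tables can show, but does not justify leaving them out.

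**Conclusion.** The point holds as a reporting gap of low priority. SAP 4.6.4 summarises five of seven protocol-defined vital signs, so the safety endpoint in Protocol 2.2 is only partly covered. It also specifies no age-referenced abnormality table for a population running from birth to 17 years. Individual values are not lost. Sample size, error rates, efficacy and PK are unaffected, and the study is descriptive throughout.

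The comparison of lists rests on the text alone, reading the SAP sentence as a closed list, which is its plain meaning. The dilution figures rest on the assumed change of 20 to 40 mmHg and the planned cohort sizes, and are illustrative only.

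**What to change.** In SAP 4.6.4:

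- Add height/length and weight, summarised over time as change from baseline and as age- and sex-standardised scores against a named growth reference.
- Add the number of patients with any post-baseline blood pressure, pulse or respiratory rate outside a named age-specific reference range. For low systolic pressure the limits in Protocol Appendix 6 may serve as a descriptive threshold, with a note that the protocol gives them for diagnosing anaphylaxis.
- Keep the mean-change tables.

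The cost is SAP wording and two or three descriptive tables. Height/length, weight and the other signs are already entered in the eCRF, and age and sex are recorded under Protocol 4.7.2. Visits, dosing and sample size do not change. The downside is that a growth reference and age-specific ranges for pulse, respiratory rate and high blood pressure must be chosen, because the documents supply none. Results for the few children under 2 years and for Cohorts B and C will be descriptive only, and without a control arm the standardised scores cannot attribute any change to treatment.
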